- Review of referenced studies in a large meta-analysis published by Hole et al¹¹ produced a heterogeneous population and varied results and sample sizes.
- The most reliable statistics appear to be in a paper by Cutshall¹⁶ et al, which reported results of an intervention of music for cardiac surgery patients in the ICU. The data demonstrates a narrow standard deviation and results in agreement with overall conclusion of the meta-analysis
 - Decrease in mean pain score was 1.4cm for their music group and 0.4cm for the control group, with a difference of 10mm between the groups (SD was 1.4).
- This study was therefore selected for calculation of our sample size.
- We powered our study to detect a difference of 10mm in the postoperative VAS score between intervention and control groups. We deem this reasonable considering the review article by Hole¹¹ reporting on 73 randomized trials, found a mean overall difference in pain scores of 23mm between intervention and control groups.
- Power Analysis
 - Our calculation demonstrated need to enroll 43 patients in each arm based on the following:
 - A difference of 1cm on subjects' VAS scores for pain
 - Power at 90%
 - Standard deviation at 1.4
 - Effect size at 0.714

- Assuming an estimated loss rate of 15%, the number of patient enrollment per arm was set to 51, for a total of 102 patients. [Attrition calculation: (43/0.85)]
- This study met challenges with personnel shifts within Hatton Institute that impacted data collection. Following review, hiring of new staff and re-training, we determined to perform an interim analysis. Of the 52 subjects enrolled since restructuring, 42 have completed follow-up. This interim analysis reveals a true attrition rate of 20%; five percent higher than the original 15% used in the power calculation. Assuming this loss rate remains constant through the close of the study, in order to reach significance, we will need to enroll an additional 27 subjects above the planned 102. For sake of randomization, we have set new total enrollment to 132.
- Subjects will be randomized by using a random numbers table and sealed sequential envelopes prepared by an independent statistician.
- **Data Collection**
 - Primary outcome:
 - VAS scores for pain “right now” and “most intense pain” [0-100mm], administered following breakfast on post-operative day one, comparing intervention and control groups
 - Secondary Outcomes:

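### The stated 20% loss rate does not yield 27 extra subjects: the plan's own formula gives 6 (108 in total), not 129 set to 132

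*Combined protocol and SAP*

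**What the plan says.** All the figures are in the Power Analysis bullets under Sample Size (Research Plan, Participants).

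- The base requirement is 43 per arm: "Our calculation demonstrated need to enroll 43 patients in each arm". It is for a 1 cm difference, a standard deviation of 1.4, an effect size of 0.714 and 90% power.
- The allowance for loss is "Assuming an estimated loss rate of 15%, the number of patient enrollment per arm was set to 51, for a total of 102 patients", with the formula printed as "Attrition calculation: (43/0.85".
- After a change of research staff, the plan gives an interim count: "Of the 52 subjects enrolled since restructuring, 42 have completed follow-up". It concludes: "This interim analysis reveals a true attrition rate of 20%; five percent higher than the original 15% used in the power calculation".
- The consequence is worded as "Assuming this loss rate remains constant through the close of the study", followed by "in order to reach significance, we will need to enroll an additional 27 subjects above the planned 102". The last step is "For sake of randomization, we have set new total enrollment to 132".

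No calculation is shown for the 27. No other input is revised: the difference, standard deviation, power and number needed per arm stay as they were.

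**The concern.** A rise in loss from 15% to 20% is a small change, and it should move the enrolment target by only a few subjects. An increase of 27 on 102 is more than a quarter. The bullet gives the loss rate as its only reason, and the formula for turning a loss rate into an enrolment figure is printed just above it, so a reader should be able to reproduce the number.

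Two things are at stake. First, the target was raised during the study, after what the plan calls an interim analysis. A change of that kind should be reproducible from its stated reason, and the power it gives should be stated. Second, the wording presents the increase as a way to reach significance. An allowance for loss keeps the planned power and cannot promise a significant result. Next to a mention of an interim analysis, the phrase invites the reading that enrolment was extended to obtain one.

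**Working it through.** **Inputs, all from the Power Analysis bullets:** 43 evaluable per arm (86 in total); difference 1 cm and SD 1.4 cm, so d = 1/1.4 = 0.714; power 90%; planned loss 15%; revised loss 20%; 42 of 52 with completed follow-up; stated increase 27; new total 132. Alpha is not given. Two-sided 0.05 is assumed, and only the power figures depend on it.

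**1. Reproduce the plan's base figures.**
- Two-sample t-test, noncentral t, d = 0.714: 42 per arm gives power 0.899 and 43 per arm gives 0.906. The plan's 43 is reproduced.
- Enrolment per arm = n/(1 − loss) = 43/0.85 = 50.6, so 51 per arm and 102 in total. This is also reproduced.

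**2. Apply the same formula at the revised rate.**
- At 20%: 43/0.80 = 53.75, so 54 per arm and 108 in total. 108 − 102 = **6**.
- At the unrounded rate: 10/52 = 19.2% not completed, and 43/(42/52) = 53.2. Again 54 per arm and 108 in total.
- Stated: 102 + 27 = 129, set to 132. The gap is 129 − 108 = 21 before the final rounding and 132 − 108 = 24 after it.

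**3. Loss rate implied by the stated totals, if 86 are to remain.**
- 129: 1 − 86/129 = 33.3%.
- 132: 1 − 86/132 = 34.8%.

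**4. Look for another route to 129.**
- Inflating the already inflated figure: 102/0.80 = 127.5, so 128; by arm, 51/0.80 = 63.75, so 64 per arm and again 128. This counts loss twice, because 102 already contains the 15%, and it falls one short of 129.
- The same route with 42/52: 126.3 in total, or 63.1 and so 64 per arm (128).
- Multiplying instead of dividing: 43 × 1.20 = 51.6, so 52 per arm and 104 in total.

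The double inflation comes nearest of these, but nothing in the document confirms it.

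**5. What each total delivers, if 20% loss applies to everyone enrolled.**

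| Enrolled | Completers (× 0.80) | Per arm | Power |
|---|---|---|---|
| 102 | 81.6 | 40.8 | 89.0% |
| 108 | 86.4 | 43.2 | 90.7% |
| 129 | 103.2 | 51.6 | 94.9% |
| 132 | 105.6 | 52.8 | 95.3% |

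The requirement is 86 completers. At 20% loss, 129 enrolled leaves about as many completers as the 102 that were to be enrolled, which is not what the power calculation asks for.

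**The case against.** The strongest reply is that the 27 may not come from the loss rate alone. The bullet opens with staffing problems that affected data collection, and it counts loss only among subjects enrolled after the restructuring. If earlier subjects have no usable data, more replacements are needed. The 52 recent subjects gave 42 completers, so 86 − 42 = 44 are still needed, and 44/0.80 = 55 must be enrolled. That makes 52 + 55 = 107 enrolled since the restructuring. With 129 − 107 = 22 earlier subjects wholly lost, the total is exactly 129; with 132 − 107 = 25, it is 132. In the latter case the expected completers are 42 + 55 × 0.80 = 86, which gives the planned 90% power and no over-enrolment.

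This stands as a possibility, and it limits what can be claimed. The 95% power figure holds only if 20% loss applies to all 132, and 108 should not be read as the only right target. It does not rescue the sentence: the document gives no count of earlier or unusable subjects and ties the increase to the 20% rate alone. If unusable data are the reason, that is a material fact and the plan should state it.

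Two smaller replies have some force. The plan does not say whether the 10 of 52 were lost or still awaiting the two-week visit, and the primary outcome is taken on postoperative day one, so incomplete follow-up may overstate loss for the primary analysis. A lower loss rate would call for fewer extra subjects, which widens the gap. The rounding to 132 is explained by randomisation, but that covers 3 subjects, not the 21 between 108 and 129.

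**Conclusion.** The concern holds. By the plan's own formula and its own 20% rate, the increase is 6 subjects (108 in total), not 27 (129, set to 132). This result starts from the printed 43 per arm and needs no assumption about alpha.

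The power figures assume a two-sided 0.05 test, a 10 mm difference, an SD of 14 mm and 20% loss among all subjects. On those terms 132 gives about 95% power where 90% was planned. The discrepancy is then towards over-enrolment, with no bias and no loss of power. What is shown is that the stated reason does not yield the stated number, not that 132 is an unsuitable target. It should be corrected, because the trial's enrolment target rests on this sentence.

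**What to change.** Establish how the 27 was obtained, then rewrite the bullet so that the figure matches its basis. One of these will apply:

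- If the loss rate is the only reason: *43/0.80 = 53.75, rounded up to 54 per arm, 108 in total, to keep 90% power.*
- If 132 is kept and 20% loss applies to everyone: *at 20% loss, 132 enrolled gives about 53 evaluable per arm and about 95% power (10 mm difference, SD 14 mm, two-sided 0.05).* Alpha would need to be confirmed, since the plan does not state it.
- If 132 also replaces earlier subjects whose data cannot be used: state how many there are, the expected number evaluable per arm, and the resulting power.

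In each case, replace the words about reaching significance with *to keep 90% power*, or with the power actually obtained.

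The cost is the wording of one bullet. Enrolment can stay at 132 if its basis and power are stated. The document does not give total enrolment to date, so whether 108 is still an available target is for the investigators to say.

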- Additionally, the room will be decorated with a wall hanging image of a soothing nature landscape. The landscape will be hung on the wall near the foot of the bed throughout the participant's length of stay.

- Control group:

- Those patients randomized to experience an un-modified post-operative environment will experience a private hospital room at Good Samaritan or Bethesda North hospitals without alteration.
- On POD 1, following breakfast, patients will be asked to rate their pain using a VAS scale from 0-100 mm.
- Prior to discharge they will complete a second VAS regarding their current pain. They will also complete VAS questions regarding satisfaction and overall pain during their hospital stay.
- They will be asked two modified questions similar to the Hospital Consumer Assessment of Healthcare Providers and Systems survey (HCAHPS) to determine perception of care. A modification is necessary because these questions cannot be utilized while patients remain admitted to the hospital per federal regulation.
- They will be asked two questions regarding overall perception of care (VAS 0-100mm)

- The intervention group will also be asked regarding their appreciation of music, and the landscape as a part of their healing experience.
- At their 2 weeks postoperative follow-up appointment, they will be provided similar VAS questions for satisfaction and pain, followed by the unmodified HCAHPS questions. They will also be asked to report their overall satisfaction with the results their surgery and their decision to have surgery.
- The intervention group will be asked similar questions regarding their experience with music and landscape during their recovery.
- Demographics, medical and surgical information, complications, postoperative narcotic use, voiding trial results, CBC, etc will be recorded from their chart.
- Post-operative orders will be completed through a standardized order set which provide the standard of care for the post-operative management of patients having vaginal reconstructive surgery. There will be no differences in these orders between intervention and control group with exception of the music and landscape.

- **Participants**

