 - VAS pain scores prior to discharge based on the validated SPS pain questions²⁵.
 - VAS for satisfaction with their hospital stay prior to discharge
 - Nursing recording pain scores prior to delivery of pain medications (recorded in Epic)
 - Total morphine equivalents during hospital stay

- Patient reported impression of the music and art using Likert scales, at discharge and 2 weeks post operatively for the intervention group
- Patient impression of the hospital based on responses from modified HCAHPS questions prior to discharge on post-operative day one:
 - First Question in VAS format: “Compared to other hospitals, how would you rate this hospital”?
 - Second Question in VAS format: “How likely are you to recommend this hospital to family and friends?”
- Patient VAS scores concerning their perception of the healing environment of the hospital and whether they would choose the hospital again
- Responses at the 2 week postoperative appointment to another identical series of VAS for satisfaction and pain, questions 21 and 22 from the HCAHPS survey, a question on pelvic symptoms after surgery, and the validated Decision Regret Scale for pelvic floor disorders²⁴
- General Demographic Data
 - Age, BMI, race, history of depression, home medications, sexual activity, alcohol use, prolapse stage, procedures performed, voiding trial results, length of stay, surgical and postoperative complications, and estimated blood loss
- *VAS Score Validity:*
 - The VAS score is a well-established tool for measuring a patient’s pain level that has been in clinical practice for decades. This tool has been applied throughout the medical field as a standardized measure of pain and remains a common method of characterizing pain levels by researchers. It has been shown to be reliable in the assessment of acute pain¹⁸.
- *HCAHPS survey questions:*
 - Survey is the first national, standardized, publicly reported survey of patients' perspectives of hospital care. HCAHPS (pronounced “H-caps”),

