- **Statistical Analysis**

- Descriptive statistics will be calculated for all continuous and categorical data. Continuous variables will be summarized as mean (SD) or median (range). Categorical variables will be presented as frequency (Percentage). The primary outcome is the VAS scores for pain in the morning of post-op Day 1 (POD 1). Student's t-test or Mann-Whitney U test (Wilcoxon Rank Sum test) will be implemented to test for significant difference in pain and satisfaction scores and narcotic use between intervention and control groups. Assumptions will be examined and appropriate parametric or non-parametric tests will be used. For categorical data, Chi-square or Fisher's exact test will be employed to test the association.

Ethical Considerations

- **Informed consent**

- Patients who agree to participate in the study will sign a written informed consent. They will be consented by one of the stated investigators or trained Research Nurse and they will receive a copy of the signed informed consent statements (ICS). A copy will be put in their medical file.
- **Privacy information**
 - Extensive efforts will be made to ensure participant confidentiality and prevent unauthorized release of personal information. Electronic study documents will be stored on a secure drive and hard copy documents stored in a locked area. Thereby, all identifying and protected health information, including name and date of birth, will be maintained in a secure area at all times, accessible by authorized personnel only.
 - All communication between staff members regarding participant data will occur via the Subject ID number only. However, identifying information will be retained in the original/source documents.
 - The participant will be logged in the Excel spreadsheet and assigned a Subject ID number. Each participant will be assigned the next available Subject ID number. Once each Subject ID number has been assigned, it will not be reassigned.
 - Study documentation, both electronic and hard copy will be stored securely for ten years and then destroyed.
- **When and how will results be disseminated?**
 - We plan for the results to be disseminated in Spring 2020 at a national meeting in the form of a poster or oral presentation. We also plan for the results to be published.

References

1. Nightingale, F. Sick nursing and health nursing. Summary. Chicago: The International Congress of Charities, Correction and Philanthropy. 1893.

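### Nurse pain scores taken before a medication are observed only when a dose is delivered, so a between-arm test of them is open to selection after randomisation

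*Combined protocol and SAP*

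**What the plan says.** The list of secondary outcomes under Data Collection includes "Nursing recording pain scores prior to delivery of pain medications (recorded in Epic" and, as a separate item, "Total morphine equivalents during hospital stay". The Statistical Analysis section says that a t-test or Mann-Whitney test "will be implemented to test for significant difference in pain and satisfaction scores and narcotic use between intervention and control groups". It does not name the nurse scores separately from the other pain scores.

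The Background cites earlier work in which music lowered analgesic use and landscapes lowered opiate use. The Intervention and Control group text says that "Post-operative orders will be completed through a standardized order set", identical in both arms apart from the music and the landscape.

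The documents do not state:
- whether pain medication is scheduled or given on request;
- how many nurse scores a patient may have, or on what scale;
- which score or summary enters the test;
- how a patient with no score is handled.

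**The concern.** A score that is defined by delivery of a dose is conditioned on something that happens after randomisation. The plan treats narcotic use as an outcome that may differ between arms, and its Background gives reasons to expect less of it with the intervention. So the number and timing of nurse scores may also differ by arm. A patient in little pain gives few scores or none, and those she does give come from her worse moments.

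The result will be read beside the VAS and morphine results. A near-null comparison here could wrongly contradict a real VAS benefit. A difference caused only by a change in when patients ask for medication could be taken for a change in pain. Leaving the summary open (first, mean or maximum score) also allows the choice to be made after the data are seen.

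**Working it through.** **1. The plan's own figure.** No sample size is given for the nurse scores. The stated 43 per arm belongs to the primary outcome: "A difference of 1cm on subjects' VAS scores for pain", SD 1.4 cm, power 90%, with two-sided alpha 0.05 assumed. The normal approximation is 2 × (1.960 + 1.282)² × 1.4² / 1² = 41.2, so 42. The exact t-test solution is 42.17, so 43. Then 43/0.85 = 50.6, so 51. Both stated figures reproduce. I use 43 per arm below.

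**2. Selection.** From the plan: a 10 mm effect and 43 per arm. Assumed, because the documents give nothing: a 0-100 mm scale, control mean 40 mm, between- and within-patient SD 14 mm each, 10 pain checks per patient, and a score recorded only when pain reaches a trigger. Each patient's recorded scores are averaged; patients with none drop out.

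| Trigger | Expected arm difference | Power |
|---|---|---|
| none (every check recorded) | 9.5 mm | 87% |
| 30 mm | 4.4 mm | 66% |
| 40 mm | 2.9 mm (2.8 to 2.9 across runs) | 42% |
| 50 mm | 1.8 mm | 19% |

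The first row is 9.5 rather than 10 mm because scores are cut off at the ends of the scale. At the 40 mm trigger about 9% of controls and 24% of treated patients have no score.

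A second model used 8 checks, total SD 14 or 25 mm, intraclass correlation (ICC) 0.5, and sharp or gradual triggers between 20 and 50 mm. A true 10 mm effect appeared as 1.4 to 8.7 mm (SD 14) or 2.1 to 7.4 mm (SD 25). The direction is the same throughout; the size depends on the trigger.

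**3. Only request behaviour changes.** In the second model, give both arms the same pain (mean 40 mm) and let intervention patients receive a dose at 40 mm instead of 30 mm. Their recorded scores then look 1.8 to 5.9 mm worse, although pain does not differ.

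**4. Scheduled dosing.** If every dose is given by the clock, recording does not depend on pain and the shrinkage is nil.

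**5. Repeated records, if pooled.** With m records per patient entered as independent observations, the false-positive rate is 2 × [1 − Φ(1.96 / √(1 + (m − 1) × ICC))].

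| m | ICC | 1 + (m − 1) × ICC | 1.96 / √ | False-positive rate |
|---|---|---|---|---|
| 2 | 0.1 | 1.1 | 1.869 | 6.2% |
| 4 | 0.3 | 1.9 | 1.422 | 15.5% |
| 6 | 0.5 | 3.5 | 1.048 | 29.5% |

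With one mean per patient, the simulated rate was 4.2% to 5.6%. The values of m and ICC are assumptions.

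**The case against.** Several stronger readings are tempting, and the documents do not support them.

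- *The plan inflates type I error by pooling records.* Nothing says that individual records will be entered as independent observations. A t-test or Mann-Whitney test on one value per patient fits the text equally well and holds its level. What stands is a missing definition: the plural wording implies repeated records, and no reduction to one value is given. The stay may also be short, since the modified HCAHPS questions are placed before discharge on POD 1, so records may be few.
- *No other nurse scores exist.* The protocol says which scores are used, not that Epic holds no others.
- *The plan hypothesises lower narcotic use.* Its hypotheses concern VAS pain, satisfaction and recommending the hospital. Narcotic use is a compared outcome, and the Background makes an effect on it plausible. That is enough for the concern, but it is not a stated hypothesis.
- *Selection alone creates false positives.* It does not if the intervention changes neither pain nor requests for medication.

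It is also fair to object that the size of the selection rests on assumed inputs and on a dosing regime the documents do not state, and that the trial was never powered for this outcome. Both objections stand. They limit the numbers, not the structural point, which follows from how the outcome is defined.

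**Conclusion.** The point holds for this secondary outcome as defined. To the extent that doses depend on pain, a between-arm test of pre-medication scores compares selected moments in selected patients and will usually understate a real benefit. Under the assumptions in the working, less than half of a true 10 mm effect remains at triggers of 30 to 50 mm. Softer or lower triggers keep more of it, and purely scheduled dosing keeps all of it. A change in request behaviour alone can produce a spurious difference.

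The handling of repeated records is unspecified rather than wrong, and false-positive inflation is a risk only if the analyst pools. The POD 1 VAS, the pre-discharge VAS and total morphine equivalents are not defined by delivery of a dose, so the primary outcome and the sample size are untouched. This should be corrected, but it does not threaten the main result.

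**What to change.** In the Statistical Analysis section, define one value per patient: the mean of the nurse scores charted in Epic within fixed time windows, whether or not a medication was given. Average within each window first and then across windows. A single mean of all charted scores would still give extra weight to the high-pain moments of patients dosed more often. State how a patient with no score in a window is handled, and say that individual records will not be entered as separate observations in a t-test or Mann-Whitney test.

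If only pre-medication scores are charted, report them descriptively beside morphine equivalents, with the number of records and the number of patients with none in each arm, and do not test them as a treatment effect. Settle this before the nurse scores are examined by arm.

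The cost is a few lines of text and a slightly wider chart pull. If routine scores are not charted, one inferential secondary comparison is lost. No extra patient contact is needed.

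### The 2-week pain and satisfaction VAS are tested on responders only, although the same scales were scored before discharge; a mixed model would protect these secondary comparisons cheaply

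*Combined protocol and SAP*

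**What the plan says.** All references are to the combined protocol and SAP.

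- **Pain VAS.** It is taken after breakfast on postoperative day 1 (POD 1), which is the primary time point. The Research Plan then states: "Prior to discharge they will complete a second VAS regarding their current pain".
- **Satisfaction VAS.** The secondary outcomes under Data Collection include "VAS for satisfaction with their hospital stay prior to discharge".
- **Two weeks.** The same list includes "Responses at the 2 week postoperative appointment to another identical series of VAS for satisfaction and pain". The Research Plan calls these 2-week questions only similar.
- **Analysis.** For these scores the Statistical Analysis section names one method: a "t-test or Mann-Whitney U test (Wilcoxon Rank Sum test) will be implemented to test for significant difference in pain and satisfaction scores". It gives no repeated-measures model, no adjustment for an earlier score, no analysis population and no missing-data rule.
- **Loss.** Under Power Analysis: "Of the 52 subjects enrolled since restructuring, 42 have completed follow-up". The plan states this as 20% attrition and responds by raising enrolment from 102 to 132.

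**The concern.** A two-sample test of a 2-week score can use only women who have that score. A woman who answered before discharge and did not return contributes nothing to the 2-week comparison, although her earlier answer is informative about the missing one. Enrolling more women restores precision, but it does not correct for selective return.

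Selective return is plausible here. Women know whether they have the speaker and the landscape print, the intervention is meant to change the very scores that may influence return, and the 2-week answers are collected at an appointment. Satisfaction is a stated secondary aim and hypothesis, so a shifted 2-week difference or a wrong error rate would affect a claim that the sponsor intends to make.

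**Working it through.** **Plan's own figure.** With a difference of 1 cm and SD 1.4 cm, the effect size is 1/1.4 = 0.714. A two-sided 5% t-test (alpha is not stated; this value is assumed) needs 42.2 per arm for 90% power. That rounds up to 43, with power 90.6%. Then 43/0.85 = 50.6, or 51 per arm. Both figures reproduce.

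**Inputs for this point.**
- 132 enrolled, taken as 66 per arm (equal allocation).
- Loss: (52 − 42)/52 = 19.2%, stated as 20%. Of 132 women, 132 × 0.8 ≈ 106 remain, about 53 per arm.
- SD 14 mm. The plan takes this from a pain study in cardiac surgery; using it for satisfaction is an assumption.
- Correlation ρ between discharge and 2-week scores: not in the documents; 0.3 to 0.7 assumed.
- Loss depends on the discharge score z (in SD units) through a logistic rule with slope s, p(z) = 1/(1 + exp(−(a + s·z))), with a set so that 20% are lost.

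**Bias.** With equal SDs at both times,

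bias = ρ × (shift in one arm − shift in the other),

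where shift is the mean discharge score of women who return minus the mean of all women in that arm: 14 × E[z·(1 − p(z))]/0.8. Numerical integration gives shifts of 1.35, 2.43 and 3.17 mm in size for s = 0.5, 1.0 and 1.5. If the arms share the rule and the discharge mean, the two shifts cancel.

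Simulated bias of the responders-only difference (5,000 trials per scenario, slope 1 per SD), in mm:

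| Loss rule | ρ = 0.3 | ρ = 0.5 | ρ = 0.7 |
|---|---|---|---|
| Same in both arms, no arm difference before discharge | about 0 | about 0 | about 0 |
| Same in both arms, 10 mm arm difference before discharge (overall loss about 16%) | 0.2–0.3 | 0.5 | 0.7 |
| Depends on score in one arm only | 0.7–0.8 | 1.1–1.2 | 1.7 |
| Opposite dependence in the two arms | 1.4 | 2.5 | 3.4 |

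The formula agrees. For one arm only, 2.43 × 0.3, 0.5 and 0.7 = 0.73, 1.2 and 1.7. Opposite dependence doubles these.

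**Error rate at ρ = 0.6, no true effect.** The responders-only SE is 14 × √(2/52.8) = 2.72 mm. Rejection is about Φ(−1.96 + b/SE) + Φ(−1.96 − b/SE), where b is the bias:
- one arm only, slope 1.0: b = 0.6 × 2.43 = 1.46 mm, rejection 8.4%
- one arm only, slope 1.5: b = 0.6 × 3.17 = 1.90 mm, rejection 10.7%
- slopes 1 and −0.5: b = 0.6 × (2.43 + 1.35) = 2.27 mm, rejection 13.3%

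Simulations gave biases of about 1.4 to 2.3 mm and rejection of about 8 to 14%. A two-visit likelihood estimator, which is what a mixed model uses here, was unbiased to about 0.1 mm and rejected in 4.2 to 5.6% of trials.

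**A true 8 mm effect, shared loss rule, ρ = 0.6.** The responders-only estimate was about 7.5 mm (slope 1.0) or 7.3 mm (slope 1.5), a shrinkage of about 0.5 to 0.7 mm. The model returned 8.0 mm.

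**Precision under random loss.** The model's SE is 14 × √(2/66) × √(ρ² + (1 − ρ²)/0.8).
- ρ = 0.3: 2.70 mm, about 1% below 2.72
- ρ = 0.5: 2.66 mm, about 2.5% below
- ρ = 0.6: 2.62 mm, about 4% below
- ρ = 0.7: 2.59 mm, about 5% below

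At ρ = 0.6, power for 8 mm goes from about 83% to 85–86%.

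**The case against.** The strongest reply has several parts, and much of it stands.

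- **Dependence of loss on earlier answers is not enough for bias.** A reader might infer that it is. The first row of the table shows otherwise, and nothing in the documents shows that loss differs by arm. The inflated error rates arise only under arm-specific loss.
- **The 20% is not a count of women with discharge scores and no 2-week scores.** A reader might infer that a fifth of the women's discharge answers are discarded. The plan does not say when the 10 women were lost, whether they had answered before discharge, or whether some were still awaiting follow-up. It applies the same rate to sample size for a POD 1 outcome, so some may have been lost earlier. The discharge answers are also compared in their own right as secondary outcomes.
- **Little power is lost.** This stands: the SE falls by at most about 5%, and every bias in the table except that for opposite dependence at ρ = 0.7 is below the SE of about 2.7 mm.
- **The items may not match.** The Research Plan and Data Collection describe the 2-week questions differently. POD 1 asks about pain now and most intense pain, while the Research Plan's discharge items are current pain and overall pain during the stay. The items must be matched before a model can be specified.
- **A normal model suits bounded, skewed scores poorly.** The planned choice between a t and a rank test does allow for this. In a check with ceiling-skewed scores the model kept its advantage, which answers most of the objection but not all of it.

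What remains is that the plan has noticed the loss, holds data that would guard against its main risk, and does not use them.

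**Conclusion.** The point holds as a cheap improvement to the 2-week secondary VAS comparisons. Those comparisons are exposed to bias if loss depends on the discharge score and the arms differ either in that score or in the dependence. The null bias under arm-specific loss is about 0.7 to 3.4 mm, against a 10 mm target difference. It is about 0 when the arms share both the loss rule and the discharge mean. The sizes rest on 66 per arm, SD 14 mm, 20% loss taken at its upper limit, and an assumed correlation.

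The case for the change is protection from bias; the gain in precision is minor. A reader might also infer that the main result is at risk. It is not: the primary outcome is POD 1 pain, and neither it nor the pre-discharge comparison depends on return at 2 weeks.

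**What to change.** 1. Reconcile the Research Plan and Data Collection descriptions of the 2-week questions, and list the VAS items asked in the same form before discharge and at 2 weeks (and on POD 1 where the item matches).
2. In Statistical Analysis, analyse each matched item with a repeated-measures mixed model: arm, time, arm × time and unstructured covariance, including every randomised woman with at least one score. Report the arm difference at each time with a 95% CI.
3. Report the number lost by 2 weeks in each arm.
4. Keep the planned t or Mann-Whitney test on responders as a sensitivity analysis, including for skewed scores.
5. Leave the POD 1 primary analysis unchanged, and leave HCAHPS questions 21 and 22 as planned, because their pre-discharge versions use a different response scale.

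The cost is a few lines of text and standard software, with no new data or visits. The model assumes that loss is explained by arm and the observed scores, which is weaker than what the responders-only test needs but cannot be verified. It also applies a normal model to bounded scores. The wording should be settled before any comparison of the arms.
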